Safety of a Sheath Cryoprobe Bronchoscopic Transbronchial Biopsy Technique

NCT04486560

Document Creation Date: October 1, 2020

Safety of a Sheath Cryoprobe Bronchoscopic Transbronchial Biopsy Technique
ACRONYM : FROSTBITE

Principal Investigator: [name]

Draft or Version Number: v.0.8
01 Oct 2020

STATEMENT OF COMPLIANCE

The trial will be conducted in accordance with the ICH GCP E6, the Code of Federal Regulations on the Protection of Human Subjects (45 CFR Part 46), and the STTR Terms of Award. The Principal Investigator will assure that no deviation from, or changes to the protocol will take place without prior agreement from the sponsor and documented approval from the Institutional Review Board (IRB), except where necessary to eliminate an immediate hazard(s) to the trial participants. All personnel involved in the conduct of this study have completed Human Subjects Protection Training.

I agree to ensure that all staff members involved in the conduct of this study are informed about their obligations in meeting the above commitments.

Principal Investigator: _____

Print/Type Name

Signed: _____ Date: _____

Signature

STUDY CONTACT INFORMATION

Coordinating Center	Core Lab

Johns Hopkins University
 
Principle Investigator (Lead PI):
 
[name], DO Associate Professor of Medicine Johns Hopkins University [contact] Email: [contact]
 
Research Coordinator:
 
[name] Research Program Manager [contact] Email: [contact]
	
Pathology: [name] Associate Professor of Pathology Johns Hopkins University [contact]
 
Radiology: [name] Associate Professor of Radiology Johns Hopkins University [contact]

Additional Site Contact	

[name] Associate Professor of Medicine Vanderbilt University [contact] Email: [contact]
	

PROTOCOL SYNOPSIS

Title:	Safety of a Sheath Cryoprobe Bronchoscopic Transbronchial Biopsy Technique (The FROSTBITE Trial)
Study Objective:	To determine the safety profile of a 1.1mm flexible single-use cryoprobe with oversheath used for transbronchial lung biopsy via a bronchoscopic approach
Study Device:	ERBE 1.1mm flexible single-use cryoprobe with oversheath
Design:	A multi-center, non-randomized, single-arm, prospective trial designed to determine the safety profile of a novel cryoprobe and generate preliminary efficacy data.
Phase:	Post-Market
Number of Sites enrolling participants:	2
Number of Subjects:	50
Study Participant Duration:	30 days
Study Duration:	3 months
Population:	
Inclusion Criteria:
 
 • Male or Female, \geq 18-years-old • Scheduled to undergo bronchoscopy with transbronchial biopsy as the standard medical care determined by their treating pulmonologist 
Exclusion Criteria:
 
 • Pregnant or nursing females, or females of child bearing potential who refuse to take a pregnancy test prior to enrollment • Individuals with current or recent systematic conditions, such as uncontrolled hypertension (systolic $>$ 200 mmHg or diastolic $>$ 110 mmHg), type 1 diabetes, severe pulmonary hypertension, acute kidney injury, stroke (within the last 6 months) or myocardial infarction (within the last 3 months) • Presence of bleeding disorder • Platelet count $<$ 50,000 • Current use of systemic anticoagulation or antiplatelet therapy without the ability to hold therapy for the recommended amount of time prior to an invasive procedure (aspirin monotherapy is acceptable)

	
 • International Normalized Ratio (INR) <1.5 • Robotic Bronchoscopy • Do Not Resuscitate (DNR) status • Do Not Intubate (DNI) status
Endpoints:	
The primary endpoint will be the number of serious adverse events in those enrolled in the study. Serious adverse events are defined as:
 
 • Grade 3 or 4 bleeding • Pneumothorax requiring chest tube placement (Grade ≥ 2) • 30-day respiratory failure and death. 
Secondary endpoints include minor adverse events (bleeding Grade 1 or 2), pneumothorax not requiring chest tube placement (Grade 1), histologic accessibility, diagnostic yield

Statistical Methodology	This study is designed to ensure the serious adverse event rate using the 1.1mm flexible single-use cryoprobe with oversheath will not exceed the expected serious adverse event rate of transbronchial biopsy using standard biopsy procedures (30%)
Safety Monitoring	After each 10 consecutive patients are enrolled, the DSMB will review safety. Additionally, after each serious adverse event, the study will be halted until adjudicated by the DSMB.

1. BACKGROUND

The current standard method for obtaining bronchoscopic lung biopsy specimens is transbronchial forceps biopsy (FBx). However, the utility and diagnostic capability of FBx is limited by poor specimen quality due to small biopsy size, crush artifact and cellular artifact.¹ In part due to these restraints, the diagnostic yield of FBx has remained limited to 34-58% in diffuse lung disease¹⁻³ and 54-58% for pulmonary nodules^{4,5}. With the promise of obtaining higher quality tissue samples, cryoprobe biopsy (CBx) offers a similarly minimal invasive alternative to standard FBx.

Cryoprobe have been used in the bronchoscopic management of malignant endobronchial disease and for transbronchial biopsy. The CBx operates using the Joule-Thomson effect, in which compressed gas undergoes adiabatic expansion and rapidly cools the probe's tip. This allows for adequate anchoring of the probe to lung parenchyma and biopsy specimen retrieval. There have been numerous recent studies evaluating the performance of CBx. Higher diagnostic yields and larger biopsy sizes with better quality have been observed using CBx over FBx^{2,3,6-8}. However, these benefits might come at a cost of higher complication rates, specifically, higher bleeding risks.

1.1. STUDY RATIONALE

One of the drawbacks of the current available CBx system (Erbe Elektromedizin GmbH) is the need for *en bloc* removal of the cryoprobe, specimen, and bronchoscope out of the patient's airway to retrieve the sample. This timeframe when the scope is removed may increase bleeding complications usually mitigated by keeping the scope wedged after each biopsy. This necessitates a secure airway to permit rapid re-entry of the bronchoscope, and placement of a prophylactic bronchial blocker which limited this procedure to advanced bronchoscopists. To overcome this obstacle, a novel, smaller 1.1mm flexible single-use cryoprobe (SCBx) with oversheath has been developed that can retract the tissue sample through the oversheath via the working channel of the bronchoscope while the scope remains wedged in the airway. This permits a technically less cumbersome biopsy while the scope remains in place to manage potential complications. It is reasonable to hypothesize that due to these advancements in procedural technique, the safety profile of this new SCBx would be superior to traditional CBx. That said, no prospective trials have been performed evaluating the safety of the SCBx. Here, we propose the first human studies to evaluate the safety of the SCBx for bronchoscopic transbronchial lung biopsy.

1.2. DEVICE DESCRIPTION

The ERBE 1.1mm flexible single-use cryoprobe with oversheath has been approved by the US Food and Drug Agency (FDA) under a 510(k) application (ERBECRYO® 2 Cryosurgical Unit and Accessories - K190651). It is to be used with the ERBECRYO 2 unit. The ERBECRYO 2 is a device which was designed and optimized to address many of the clinical variables known to affect previous generations of the technology. This device contains an advanced flow-control system which is intended to provide optimized and reproducible CO₂ gas flow for each individual probe specification, including the miniaturized 1.1mm cryoprobe. This optimized gas flow is an important variable to support standardization of the technical and clinical performance.

The use of an oversheath with the 1.1mm single-use flexible cryoprobe enables the working channel of the bronchoscope to be protected during retrieval of cryobiopsy specimens. This enables retrieval of the biopsy specimen through the working channel of the bronchoscope in a similar fashion to transbronchial forceps, brush and needle biopsy, permitting the bronchoscope to remain in place while biopsy samples are retrieved. In this study, the 1.1mm single-use flexible cryoprobe with oversheath will be used according to the associated Instructions for Use (IFU).

1.3. PRIOR CLINICAL DATA

Preliminary studies were performed in a porcine model to better evaluate the performance of SCBx.⁶ In a prospective, randomized, single blinded study, a 1.1mm SCBx probe, 1.9mm CBx probe, and standard 2.0mm FBx forceps were compared, assessing histologic adequacy and accessibility, sample quantity and quality, and procedure time. Samples adequate for standard pathologic processing were retrieved with 82.1% of the SCBx specimens, 82.9% of the CBx specimens, and 30% of the FBx specimens. The histologic accessibility and biopsy area of both SCBx and CBx was superior to FBx (Figure 1⁶). Procedure time for FBx was faster than for both SCBx and CBx, but SCBx was significantly faster than CBx ($P < .0001$). Fluoroscopy time was lower for both SCBx and CBx compared with FBx. This preliminary study demonstrated SCBx is a feasible technique to retrieve specimens through the working channel of a bronchoscope resulting in higher quality biopsy specimens compared with FBx.

[figure not shown]

Figure 1: Comparison of histologic accessibility and biopsy area between SCBx, CBx and FBx

1.4. POTENTIAL RISKS AND BENEFITS

This is the first-in-human dedicated post-market safety study using the new 1.1mm single-use flexible cryoprobe with oversheath. Prior larger reusable cryoprobes (1.9mm, 2.4mm) of the prior generation have been shown to be safe and efficacious. The risks of using the smaller 1.1mm single-use flexible cryoprobe with oversheath are similar to use of the larger probes. The risks associated with bronchoscopy and cryoprobe transbronchial biopsy include:

- Alteration of vocal cords (hoarse)
- Hypertension
- Bronchospasm
- Injury to mouth or pharynx
- Injury to teeth or related soft tissues
- Chills/fever
- Laryngospasm
- Coughing
- Lung parenchymal infection
- COPD exacerbation
- Myocardial ischemia
- Dyspnea
- Pharyngitis
- Dysrhythmias
- Pneumonia
- Hemoptysis
- Pulmonary edema
- Empyema
- Pulmonary infiltrate
- Excessive bleeding
- Puncturing of the airway
- Thromboembolism
- Spasm of the airway

Only trained and experienced bronchoscopists will perform the study procedure.

Possible Risks of Participation in this Clinical Study

There are standard risks of participating in a research study such as accidental disclosure of subject's confidential information. Every effort will be made to protect the privacy of research subjects. Subject names and protected health information (PHI) will be kept confidential to the extent possible and as required by applicable laws and regulations. All records and data related to the study will be maintained in a secure protected space, with access restricted to study personnel only.

1.5. POTENTIAL BENEFITS

It is possible that subjects will not receive any benefits from transbronchial cryobiopsy. Subjects may benefit from optimized medical management of their disease. Potential benefits of the procedure may be increased size of the biopsy specimen, providing additional tissue for pathologic analysis. This may lead to increases in the diagnostic yield of the bronchoscopy.

2. RESEARCH DESIGN AND METHODS

This is a multi-center, non-randomized, single-arm, prospective trial designed to evaluate the safety of a novel 1.1mm single-use flexible cryoprobe with oversheath. Consecutive patients who have been referred for transbronchial biopsy by their treating pulmonologists will be enrolled. Transbronchial biopsy will be performed using the ERBE 1.1mm single-use flexible cryoprobe with oversheath together with the ERBECRYO 2 unit.

2.1. OBJECTIVE AND PURPOSE

The objective of this study is to evaluate the safety profile of the new 1.1mm single-use flexible cryoprobe with oversheath for the sampling of lung tissue. The safety profile will be assessed across the

various indications for transbronchial lung biopsy (i.e. lung transplant rejection surveillance, lung nodule biopsy, diffuse parenchymal lung disease, pneumonitis). Safety will be assessed by collecting AE and SAE information up to 30 days.

2.2. PRIMARY SAFETY ENDPOINT

The primary safety outcome will be the proportion of participants enrolled that underwent a device related Serious Adverse Events. A complication will be considered 'device related' if it occurs following the index procedure of an attempt at cryoprobe insertion into the working channel of the bronchoscope.

A device related Serious Adverse Event is defined by the presence of any of the following:

- bleeding grade ≥ 3 (see Adverse Events for bleeding grading system)
- pneumothorax requiring chest tube placement (Grade ≥ 2 , see Adverse Events for pneumothorax grading system)
- post-procedure respiratory failure defined as the need for non-invasive or mechanical ventilation requiring ICU admission within 30 days after procedure
- Death within 30 days after procedure

2.3. SECONDARY ENDPOINTS

Secondary Outcomes will include (for definitions, see Data Collection):

- 1) Mild or Moderate Adverse Events: Rate of bleeding grade ≤ 2 , pneumothorax not requiring chest tube placement (Grade 1)
- 2) Histologic Accessibility Grade
- 3) Total Histologic area (mm^2)
- 4) Alveolated Area (mm^2)
- 5) Open alveoli percent
- 6) Percent crush artifact
- 7) Artifact free lung parenchyma percent
- 8) Activation time
- 9) Diagnostic Yield: defined as proportion of patients for which the cryobiopsy sample led to a specific diagnosis on histologic examination
- 10) Procedure time

2.4. STUDY SITE PARTICIPATION

This study will require a minimum of two participating sites. Each site will have a sufficient patient population to enroll 20-30 subjects over the enrollment period (3 months). Each site must have sufficient transbronchial biopsy volume (defined as at least 100 cases per year). To ensure adequate access to patients across the various indications for transbronchial biopsy, each site must have institutional centers for Lung Cancer, Lung Transplantation and Interstitial Lung Disease. In addition, the principal investigator and each participating co-investigator at each site must have cryobiopsy experience, defined as completion of at least 10 cryobiopsies.

2.5. SUBJECT ENROLLMENT

Patients presenting to their pulmonologist in need of a standard of care assessment of a transbronchial lung abnormality via bronchoscopic biopsy and who meet inclusion/exclusion criteria will be invited to participate. The PI will confirm subject eligibility.

Patients who sign the informed consent form will be considered enrolled. Patients who undergo bronchoscopy with at least one cryobiopsy attempt will be included within the analysis population.

2.6. PARTICIPANT INCLUSION CRITERIA

- Male or Female, \geq 18-years-old
- Scheduled to undergo bronchoscopy with transbronchial biopsy as the standard medical care determined by their treating pulmonologist

2.7. PARTICIPANT EXCLUSION CRITERIA

- Pregnant or nursing females, or females of child bearing potential who refuse to take a pregnancy test prior to enrollment
- Individuals with current or recent systematic conditions, such as uncontrolled hypertension (systolic $>$ 200 mmHg or diastolic $>$ 110 mmHg), type 1 diabetes, severe pulmonary hypertension, acute kidney injury, stroke (within the last 6 months) or myocardial infarction (within the last 3 months)
- Presence of bleeding disorder
- Platelet count $<$ 50,000
- Current use of systemic anticoagulation or antiplatelet therapy without the ability to hold therapy for the recommended amount of time prior to an invasive procedure (aspirin monotherapy is acceptable)
- International Normalized Ratio (INR) $<$ 1.5
- Robotic Bronchoscopy
- Do Not Resuscitate (DNR) status
- Do Not Intubate (DNI) status

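### The INR exclusion is reversed in both the synopsis and section 2.7: it bars patients with normal clotting and does not bar those with raised INR, in a trial whose primary endpoint includes bleeding

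*Combined protocol and SAP*

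**What the plan says.** INR is mentioned twice in the document, each time as an exclusion. In the body it sits under the heading "2.7. PARTICIPANT EXCLUSION CRITERIA" and reads "International Normalized Ratio (INR) $<$ 1.5". In the exclusion list of the Protocol Synopsis it reads "International Normalized Ratio (INR) <1.5".

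Three other criteria in the same list concern bleeding risk:

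- "Presence of bleeding disorder"
- "Platelet count $<$ 50,000"
- "Current use of systemic anticoagulation or antiplatelet therapy without the ability to hold therapy" (for the recommended period before an invasive procedure; aspirin alone is allowed)

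The list is operative. Section 2.5 says that patients "who meet inclusion/exclusion criteria will be invited to participate", and the PI confirms eligibility. The inclusion criteria in section 2.6 cover only age and a scheduled transbronchial biopsy, so they impose no INR condition that could offset the exclusion.

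**The concern.** An exclusion for INR below a threshold removes the patients whose clotting is closest to normal. Every other bleeding-related exclusion in the list works the opposite way.

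The direction matters because sections 2.2 and 5.4.2 make bleeding of grade 3 or higher a component of the primary endpoint, and the Background names bleeding as the particular risk of cryobiopsy. There are two ways a site can handle the line, and both are bad.

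- **Applied literally.** Patients with near-normal clotting are ineligible. Whoever is enrolled has been selected for impaired clotting. That is a participant-safety problem, and it would be expected to push the serious adverse event proportion upward against the 30% benchmark in section 5.4.2. The more immediate effect is that very few patients qualify.
- **Read as its opposite, or ignored.** Each enrolled patient with a recorded INR below 1.5 breaches the protocol. Section 11.2 requires each breach to be reported to the IRB, coordinating centre, sponsor and DSMB within 5 working days, and the Statement of Compliance rules out deviations without prior sponsor agreement and IRB approval, except to remove an immediate hazard. The written protocol would also still contain no INR rule that keeps out patients with raised INR.

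**Working it through.** The main check is one of logic. The plan states no figure on this point to reproduce.

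**1. The two occurrences side by side**

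| Place | List | Condition | Excluded by this line | Not excluded by this line |
|---|---|---|---|---|
| Synopsis | Exclusion | INR < 1.5 | INR < 1.5 | INR ≥ 1.5 |
| Section 2.7 | Exclusion | INR < 1.5 | INR < 1.5 | INR ≥ 1.5 |

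They agree, so neither corrects the other.

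**2. Direction compared with the neighbouring criteria**

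| Criterion | Patients removed |
|---|---|
| Bleeding disorder | Higher bleeding risk |
| Platelets below 50,000 | Higher bleeding risk |
| Anticoagulant or antiplatelet therapy that cannot be held | Higher bleeding risk |
| INR below 1.5 | Lower bleeding risk |

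A less-than sign is right for platelets, where low is dangerous. For INR the scale runs the other way: a higher value means slower clotting. The document does not state the normal INR range; that values near 1 are normal follows from INR being a ratio to normal clotting.

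**3. Could the sign be an artefact of reading the PDF?** This is unlikely. The less-than sign appears in two separately rendered places, and greater-than signs survive in the same list, as in "systolic $>$ 200 mmHg or diastolic $>$ 110 mmHg".

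**4. Illustrative effect on enrolment if applied literally**

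Inputs from section 2.4: at least two sites, at least 100 transbronchial biopsies per site per year, and a 3-month enrolment period. Input from section 5.7: 50 participants.

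- Candidates at minimum volume: 2 × 100 × 3/12 = 50.
- Assumed share with INR below 1.5: 90% to 99%. The document gives no figure for this.
- Remaining at 90%: 50 × (1 − 0.90) = 5.
- Remaining at 99%: 50 × (1 − 0.99) = 0.5.

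The 100 cases per year is a floor, so the question can also be turned round. To find 50 patients not removed by this line:

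- at 90%: 50 / 0.10 = 500 candidates in three months, or 500 × 4 / 2 = 1,000 cases per site per year;
- at 99%: 50 / 0.01 = 5,000 candidates, or 5,000 × 4 / 2 = 10,000 cases per site per year.

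These are 10 and 100 times the required minimum volume, before the other exclusions and refusals of consent.

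**The case against.** The reversal itself is hard to contest. The strongest case on the other side concerns its consequences.

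- **The two literal-use harms largely exclude each other.** If only a handful of patients qualify, the trial fails to enrol; it does not produce a biased estimate from 50 patients. This stands. Any upward bias would also count against the device under the rule that 30% or less is safe, so it would not create a false finding of safety. The harm to the few patients enrolled remains.
- **Other safeguards remain.** Some patients with raised INR would still be caught by the bleeding-disorder and anticoagulation criteria. All must already be scheduled for biopsy as standard care, and section 2.8 lets the investigator withdraw a subject whose welfare is at risk. This stands and makes the danger less direct. It does not cover every cause of a raised INR, and it does not repair the line.
- **Deviations need a recorded INR.** The protocol does not explicitly require the test, and section 3.1 has eligibility reviewed from existing records. The number of deviations is therefore unknown, and the statement has to be conditional.
- **The enrolment figure is soft.** Site volumes are floors, section 2.4 expects each site to be able to enrol 20–30 subjects, and the 90–99% share is assumed. The figure illustrates scale only. The defect does not depend on it.
- **It is probably a drafting slip that sites read correctly.** This is plausible, but the document does not show how the line was applied, and a safety criterion should not depend on staff reading it as its opposite.

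**Conclusion.** The concern holds. The INR criterion is wrong as written in both places: it runs against the three other bleeding-risk exclusions, and nothing in the document offsets it. It most likely arose in drafting, since no rationale is given for studying only patients with raised INR and section 2 describes enrolling consecutive referrals.

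Applied literally, its main effect is to make the target of 50 unreachable: about 0.5 to 5 eligible patients at minimum site volume, if 90–99% of candidates have an INR below 1.5. Those who did enter would be at higher bleeding risk in a trial that counts serious bleeding in its primary endpoint. Ignored, it turns each enrolled patient with a recorded INR below 1.5 into a reportable deviation and leaves the protocol with no working INR safeguard.

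The conclusion about direction rests only on the text and on what INR measures. The enrolment range rests on the stated assumption. The point must be fixed, because it concerns both participant safety and the definition of the study population.

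**What to change.** Amend the INR line in the synopsis and in section 2.7 so that it excludes in the same direction as the adjacent platelet, bleeding-disorder and anticoagulation criteria, and carry the change to the screening form. Reversing the sign and moving the line to the inclusion criteria would both achieve this, but they can treat a patient at exactly the threshold differently, so the amended text should say explicitly how that value is handled. The sponsor's clinicians should confirm the cut-off; none is proposed here.

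If any patients have already been screened, check how the line was applied and document any enrolments that departed from the written text.

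The cost is a correction to one line in two places and to one form, submitted as a protocol amendment to each site's IRB under section 9.2. Sample size, endpoint and analysis are unaffected.
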